Protocol Title: An extension study of intrathecal enzyme replacement for cognitive decline in mucopolysaccharidosis I

NCT number: NCT02232477

Document date: 8 May 2019

Protocol Title

Study Number MIRC-002 (100)

An extension study of intrathecal enzyme replacement for cognitive decline in mucopolysaccharidosis I

RDCRN Protocol #6728

HSC Review History

Version 2.6

Principal Investigator

[name]

1. Objectives

Safety

To evaluate the long-term safety of intrathecal recombinant human α -L-iduronidase (rhIDU), approved as Aldurazyme® [laronidase] for the treatment of cognitive impairment in patients with mucopolysaccharidosis I (MPS I).

- Evaluate the long-term safety of administering rhIDU intrathecally in MPS I subjects
- Evaluate the presence and effect of an immune response to the administered rhIDU
- Determine whether there are any other unexpected effects of rhIDU on the safety of MPS I subjects

Outcome

To evaluate the long-term effects of a limited number of intrathecal injections of rhIDU to stabilize or reverse neuropsychological deficits in non-transplanted MPS I patients.

- Neuropsychological: through an established battery of outcome measures
- Clinical: including subject reported changes, neurologic examination and walk testing ability
- Radiologic: including 3 Tesla brain MRI and diffusion tensor imaging to look at volumes, morphology, diffusion abnormalities and white matter fiber tracking.
- Biochemical: measures of GAG storage within the CSF

The primary outcome measure will be the mean intra-subject change in memory score on the Hopkins Verbal Learning Test between baseline/screening for MIRC-002 and the subject's final visit of the extension study.

2. Background

Mucopolysaccharidosis I (MPS I) is an inherited lysosomal storage disease due to deficiency of α -L-iduronidase. Deficiency or absence of α -L-iduronidase causes accumulation of glycosaminoglycans (GAG) throughout the body. Excess GAG storage causes joint pain and stiffness, difficulty breathing, valvular heart disease, and other problems leading to progressive disability and often death.

MPS I is a heterogeneous disease with several clinical phenotypes ranging from the most severe, Hurler syndrome, to the attenuated forms, Hurler-Scheie and Scheie. Patients with all forms of MPS I suffer from central nervous system disease, including cognitive decline, hydrocephalus, spinal cord compression, hearing loss, and vision difficulties. Patients with the most severe form of MPS I develop slowing in cognitive development that usually appears after age one and thereafter accelerates. By age 3 years, most of these children fall into the range of mental retardation as defined by standard intelligence tests (Shapiro and Balthazar 2000).

Although patients with milder forms of MPS I may not have grossly observable problems with cognition, these patients do have learning difficulties that are apparent in school and with neuropsychological testing. In a series of 29 attenuated MPS I patients, 34% manifested problems in speech/language development by clinical report (Vijay and Wraith, 2005). In a case study of three siblings with Hurler-Scheie, decline of cognitive function was seen on neuropsychological testing, specifically with problems encoding new information and spatial ability (Fig. 1, BJORAKER ET AL., 2005, 2006). In a study comparing Hurler patients after hematopoietic stem cell transplantation (HSCT) and Hurler-Scheie patients on intravenous enzyme replacement therapy (ERT), Hurler-Scheie patients did comparatively worse in memory and spatial testing (Shapiro et al., 2006).

An ongoing pilot study of hematopoietic stem cell transplantation (HSCT)-treated Hurler patients and ERT-treated attenuated MPS I patients (Hurler-Scheie and Scheie) is examining brain structure and function (Shapiro et al., 2007). Along with extensive neuropsychological testing, this study is employing a 3 Tesla MRI to look at volumetrics of the hippocampus compared to other regions, as well as diffusion tensor imaging and tractography to examine white matter connectivity of afferent and efferent pathways from the hippocampus to the rest of the brain. Preliminary results on neuropsychological testing support previously described findings of decline in learning and spatial ability. In attenuated MPS I patients, IQ, recognition memory and spatial working memory (controlled for IQ) correlated

with age, with older patients being more impaired. Attenuated MPS I patients were more impaired than HSCT-treated severe MPS I patients on the California Verbal Learning Test (CVLT), a test of memory encoding and spatial working memory. In addition, preliminary MRI findings demonstrate that patients with attenuated MPS I have statistically significant smaller hippocampal volumes than patients with Hurler syndrome treated with HSCT and that these hippocampal volumes correlate with functional deficit in memory. In addition, abnormal patterns of white matter diffusion have been found in both groups, with more abnormal patterns seen in the severe than the attenuated group (Shapiro et al., 2007).

[figure not shown]

Fig. 1: Memory and intelligence quotient testing in three siblings with Hurler-Scheie form of MPS I receiving intravenous rhIDU. Average decline is 2 points per year. Courtesy of [name] and [name].

Most patients with MPS I develop hydrocephalus, which is thought to be due to GAG storage in the arachnoid granulations affecting CSF reabsorption (Neufeld and Muenzer, 2001). Hydrocephalus can cause chronic, painful headaches, and may require a ventriculoperitoneal shunt to relieve pressure in the brain. In most cases, it is not the primary cause of the serious cognitive deterioration.

Hematopoietic stem cell transplantation is available to treat the brain and spinal cord as well as the physical aspects of the disease (Peters et al., 1998). However, HSCT has high rates of mortality and morbidity. A recent series of transplanted Hurler patients demonstrated a mortality of 14% related to initial transplant and 56% morbidity, which comprised acute and chronic graft versus host disease, veno-occlusive disease, and pulmonary complications (Boelens et al., 2007). HSCT is also not generally used for patients with the attenuated (Hurler-Scheie and Scheie) forms of MPS I, **even those with demonstrated cognitive defects, because little benefit for cognitive impairment has been shown in MPS I patients transplanted after age 2 years** (Whitley et al., 1993). Thus, alternative treatments for central nervous system (CNS) disease in MPS I are needed for patients who have no suitable donor, are unwilling to risk the transplant, do not qualify for HSCT, or are not completely disease-free following the procedure.

Enzyme replacement therapy given intrathecally has been shown to achieve high levels of iduronidase and reduce GAG storage in the brain, spinal cord and spinal meninges in the canine model (Kakkis et al., 2004; Dickson et al., 2007). In the brain, GAG storage levels became normal in all nineteen treated MPS I dogs (Fig. 2). When intrathecal enzyme replacement was stretched out to monthly and quarterly (every 3 months) dosing, there was no significant difference between iduronidase levels and quantitative reduction of GAG storage in the brain compared to weekly dosing.

[figure not shown]

Fig. 2: Quantitative glycosaminoglycan (GAG) storage in brain of normal dogs, untreated MPS I dogs, and MPS I dogs treated with IT rhIDU. Brain GAG levels in the IT-treated dogs reached normal levels regardless of age or treatment regimen (Dickson et al., 2007).

[figure not shown]
MPS I patients have been treated with intrathecal rhIDU for spinal cord compression as part of an earlier clinical trial (MIRC-001, BB IND 12561,

We propose an extension of our study to examine the long-term effects of intrathecal enzyme replacement on cognition. In order to document improvement with intrathecal ERT, neuropsychological testing, clinical testing, and imaging modalities will be employed. Multiple cognitive domains will be tested with an established battery of neuropsychological tests that have documented validity in patients with storage diseases (Shapiro et al., 2006). Magnetic resonance imaging of the brain will be used to document abnormalities and changes in volume and morphology. In addition, brain diffusion tensor imaging (DTI) will be employed to characterize diffusion abnormalities and perform fiber tracking. DTI and fiber tracking register diffusion patterns of water to follow axonal transport in the brain. Preliminary results in attenuated MPS I patients show DTI and fiber tracking to be abnormal in some patients (Fig. 3, Shapiro et al., 2012). DTI has been used to quantify improvement following hematopoietic stem cell transplantation in the lysosomal storage disorder, Krabbe disease (Provenzale et al., 2005).

Fig. 3: FA maps for MPS IH and MPS IA participants matched for age and gender. The figures below show the assigned colors for FA in the white matter tracts for the following directions: red = medio-lateral (left–right), green = anterior–posterior (front–back) and blue = superior–inferior (up–down). Data below the figure are from these two participants. (Shapiro et al., Mol Genet Metab 2012)

To summarize, many people with mild and moderate forms of MPS I suffer from cognitive decline, poor performance in school, and behavior difficulties. There is essentially no treatment for these problems. These patients are not candidates for hematopoietic stem cell transplantation, and intravenous enzyme replacement therapy does not treat these central nervous system symptoms. Data from the canine model of MPS I show that intrathecal rhIDU can penetrate the brain, spinal cord, and meninges, reducing GAG storage to normal levels. Data from human subjects have shown that intrathecal therapy is safe, and that it leads to clinical improvement in spinal cord compression symptoms and signs on neurologic examination. In this study, we plan to extend the evaluation of IT rhIDU to the stabilization or reversal of cognitive decline in MPS I patients.

3. Setting of the Human Research

The study will be conducted at the Los Angeles Biomedical Research Institute at Harbor-UCLA (LAB-HUCLA), Children's Hospital Oakland Research Institute

(CHORI) and the University of Minnesota (UMN). Additional study sites may be added as subjects are identified. Specific details are below:

- Recruitment: Subjects will be recruited from participants in the MIRC-002 study at LAB-HUCLA and CHORI.
- Procedures: Procedures will be performed at LAB-HUCLA, CHORI, and additional study sites that are added as subjects are recruited to the study. The addition of any new study site will be contingent upon approval by their local institutional review board (IRB), and the IRB at LAB-HUCLA. Neuropsychological testing will be performed at UMN.
- Regulations: The IRBs at CHORI and UMN will oversee the research at these respective sites, with LAB-HUCLA the primary site responsible.

4. Resources Available to Conduct the Human Research

Since subjects will be recruited from among participants enrolled in the pilot (MIRC-002) study:

- All participants are accessible for recruitment
- 67% are anticipated to be enrolled in the proposed study
- Study staff have previously been involved with participants and their families through the pilot study, so are familiar with local culture and attitudes toward clinical research.

Time requirement for the Principal Investigator to conduct and complete the proposed study within the agreed trial period is projected to be 8 hours per week.

Site study staff at the LAB-HUCLA include six members: two co-Primary Investigators, two pharmacists, one Study Coordinator, and one laboratory staff. Study staff at the CHORI site include three members: one site PI, one pharmacist and one study coordinator. Study staff at the UMN include two members: one site PI and one study coordinator. All study staff have completed appropriate training regarding protection of human research subjects, Good Clinical Practices, and HIPAA, and have previously participated in other clinical research trials.

Inpatient study treatments are conducted at the hospital in an area designated for clinical research and study evaluations are completed in separate outpatient clinical research facilities. Principal Investigators have hospital privileges at their respective sites and non-study staff resources are available at each hospital should study participants require medical or psychological support as a result of an anticipated consequence of the research study.

A site initiation meeting will be scheduled to discuss the study overview and protocol with all study staff, and to review regulatory issues, study procedures including study drug preparation, administration and accountability logging, documentation and investigators' responsibilities. As all study staff participated in the pilot (MIRC-002) clinical trial, site initiation visits will not be undertaken.

5. Prior Approvals

This study will require the following approvals prior to initiation at LAB-HUCLA:

- NIH
- IRB
- UCLA CTSI

In addition, the protocol will be filed to the Investigational New Drug Application (IND) for MIRC-002 (BB IND 104,354) at least thirty days prior to the initiation of the study.

6. Study Design

6.1. Recruitment Methods

Subjects will be recruited from participants in the pilot (MIRC-002) study. Recruitment will take place after the subject has completed the end-study visit and the investigator has deemed that the subject meets criteria for screening (see Inclusion and Exclusion criteria). Therefore, no study advertisements will be utilized for recruitment.

Subjects will be informed that financial compensation is not available and that their participation in this study is entirely voluntary.

6.2. Inclusion and Exclusion Criteria

6.2.1. Inclusion criteria

1. The subject has completed the MIRC-002 study of intrathecal enzyme replacement therapy for cognitive decline in mucopolysaccharidosis I
2. Age six years or older.
3. Subject and/or guardian willing and able to provide written informed consent.
4. Negative urine pregnancy test at screening (non-sterile females of child-bearing potential only)

5. Currently using two acceptable methods of birth control as determined by the investigator and willing to continue to use acceptable birth control during their participation in the study (non-sterile females of child-bearing potential who are sexually active only)
6. Willing and able to comply with study procedures. For example, the subjects must be able to complete written and computer-based testing. The subjects must be able to lie still in the MRI scanner for at least 40 minutes without sedation.

6.1.1. Exclusion criteria

1. The subject has undergone hematopoietic stem cell transplantation
2. Recent initiation of intravenous Aldurazyme® therapy with less than 6 months of therapy. Subjects who have been receiving Aldurazyme® therapy for more than 6 months, and those who have never received Aldurazyme® therapy, will be allowed to enroll
3. Pregnant or lactating, or considering pregnancy
4. Receipt of an investigational drug or procedure other than intrathecal Aldurazyme® within 30 days of enrollment
5. A condition, medical or other, that prevents participation in the study, including severe auditory or visual impairment, significant lumbar pathology, lumbar catheter, or recent major surgery within 6 weeks that would preclude their ability to participate.
6. Infusion reactions to intravenous or intrathecal Aldurazyme® therapy that are life-threatening or require emergent intervention such as epinephrine, cardiopulmonary resuscitation, or hospitalization
7. The subject has severely impaired spinal CSF flow, demonstrated by failure of appearance of radionuclide in the basal cisterns by 4 hours after intra-lumbar administration.
8. The subject has a coagulopathy, as identified by a platelet count of less than 50,000, an INR of 1.5 or greater, or a PTT that is 1.5 times the upper limit of normal for the laboratory from which it was drawn.

6.2. Local Number of Subjects

We expect to recruit subjects who have completed the MIRC-002 study. The total number of expected subjects in MIRC-002 is 6 subjects. Up to 6 subjects will be screened and up to 6 subjects will be enrolled in the MIRC-002(100) extension study at all sites.

6.3. Study-Wide Number of Subjects

We expect to recruit subjects who have completed the MIRC-002 study. The total number of expected subjects in MIRC-002 is 6 subjects. Up to 6 subjects will be

screened and up to 6 subjects will be enrolled in the MIRC-002(100) extension study at all sites.

6.4. Study Timelines

The duration of each subject's participation in the study is expected to be five years. We anticipate enrolling these subjects over a 4-year period. The estimated date of completion of the study is 10 years following the onset of the study.

7. Procedures Involved in the Human Research

This study is a five-year open-label, prospective trial in 6 MPS I subjects age six years or greater who have completed a 24-month open label study (MIRC-002). Potentially eligible subjects who (or, if appropriate whose parents or guardians) have provided signed, written informed consent will first participate in a baseline screening phase. This will occur at least six months after subjects have completed the MIRC002 pilot study. During baseline screening, the subjects will receive the baseline evaluations outlined below, and their eligibility will be determined. Every three months, subjects will receive intrathecal recombinant human α-L-iduronidase (IT rhIDU) approved as Aldurazyme® [laronidase] for the treatment of cognitive impairment in patients with mucopolysaccharidosis I (MPS I). Neuropsychological testing and MRI will be performed at baseline and at one year intervals. Safety will be monitored continuously throughout the subject's study participation through recording all adverse events (AEs) and periodically performing clinical and laboratory evaluations.

Study subjects will receive intrathecal enzyme therapy only during the study; intrathecal enzyme therapy will not be administered at the end of the five-year period. If further intrathecal enzyme is desired, the subject may enroll in further intrathecal research if another study is available.

To assure that subjects enrolling in the trial have maximum access to alternative therapy, subjects will be asked to receive counseling regarding other available appropriate medical and surgical alternatives prior to enrollment in this trial.

7.1. Study Rationale

In MPS I, GAG storage in the brain can cause substantial neurologic morbidity. In its most severe form, Hurler syndrome, patients are mentally retarded, but evidence of progressive cognitive decline can also be seen in patients with less severe forms of MPS I, Scheie and Hurler-Scheie syndromes. GAG storage can also obstruct CSF reabsorption with resultant hydrocephalus, which can also contribute to mental decline, in addition to causing debilitating headaches.

Treatment of the hydrocephalus often requires implanting a ventricular-peritoneal shunt to relieve CSF pressure. Currently there is no treatment for cognitive

decline in MPS I, except for early HSCT that is offered to young Hurler patients only. Essentially, patients with Scheie or Hurler-Scheie syndromes have no treatment available for cognitive decline. Intrathecal rhIDU may provide benefit for these patients for whom HSCT was not an option. It may also provide an alternative non-surgical treatment for the hydrocephalus that results from GAG storage at CSF reabsorption sites.

This study is limited to patients six years and older with milder forms of MPS I because the older and less severely affected subjects will be able to comply with the examinations and will therefore be more accurately assessed.

Neuropsychological evaluations in children younger than age six would require a different battery of tests, and therefore, the data would not be compatible. Younger children would also require general anesthesia for all of the procedures, increasing the risk to patients participating in the study. In addition, older subjects do not have HSCT as a therapeutic option. Finally, less affected MPS I patients make some enzyme on their own and may be less likely to have an immune reaction to rhIDU. For these reasons, we have selected a study population of mild to moderate MPS I patients, age six or above, with documented cognitive decline that is attributable to their disease.

7.2. Schedule of Study Evaluations

After obtaining informed consent, the investigator will conduct the study as outlined in the following sections. Table 1 summarizes the nature of the assessments and treatments and their timelines. Refer to Study Operations Manual for guidelines regarding test assessments and procedures for handling/shipment of all central laboratory samples.

Table 1 Schedule of study assessments and treatments

Month Number	Baseline	Visit 1/Odd Numbered Visits	Visit 2/Even Numbered Visits	End Study
Neuropsychological testing	X		yearly	
MRI of brain	X		yearly	
Clinical tests				
History and Physical examination	X	X	X	X
Neurologic examination	X	X	X	X
Photography and video (optional)	X	X	X	X
Six-minute walk test	X	X	X	X
Subjective response of clinical symptoms	X	X	X	X
FIM scoring	X	X	X	X

Laboratory tests (CSF)				
Protein, glucose, cell count		X	X	
GAG levels		X	X	
Anti-rhIDU antibody		X	X	
CSF iduronidase assay		X	X	
Laboratory tests (blood)				
Anti-rhIDU antibody	X	X	X	X
CBC, Chem panel 20, Coagulation studies	X	X	X	X
Neurophysiologic test				
CSF flow study	X			
Investigator Global Assessment				
	X	X	X	X
Treatments				
Intrathecal rhIDU		X	X	

Visits occur at three-month intervals starting from Visit One. There may be a variable period between Baseline/Screening and Visit One from five days to three months. If the period between Baseline/Screening and Visit One is less than one week, then all of the other assessments do not need to be repeated for Visit One.

7.3. Screening and qualification

A variable length screening phase will begin with a history and physical and neuropsychological evaluation to assess the patient for entry criteria. Patients meeting enrollment criteria will enter the study; patients not meeting enrollment criteria will not be enrolled.

7.4. Pregnancy testing

Female subjects of child-bearing potential will be required to submit a urine pregnancy test (urine beta-hCG) at baseline and at each study visit. Subjects testing positive will be withdrawn from the study. Sexually-active subjects of child-bearing potential will be required to use two acceptable methods of birth control (as determined by the investigator) during the study period.

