12.1. Adverse Events

Subjects in this study will be closely monitored during the enzyme administration and for one hour afterward with frequent (every 15 minutes) vital signs and continuous pulse oximetry. The subject will be able to contact the investigator or other appropriate personnel to report adverse events occurring later. These will be treated with appropriate medical care where applicable. Adverse events that are unanticipated will be reported within 10 working days to the institutional review board.

An adverse event (AE) is any undesirable physical, psychological or behavioral effect (an unfavorable and unintended sign, symptom or disease) experienced by a subject during their participation in an investigational study whether or not product-related. This includes any untoward signs or symptoms experienced by the subject from the time of signing of the informed consent until completion of the study. Adverse events may include, but are not limited to:

- Subjective or objective symptoms spontaneously offered by the patient or subject and/or observed by the investigator or medical staff.
- Laboratory abnormalities of clinical significance.
- Disease signs, symptoms and/or laboratory abnormalities already existing prior to the use of the study medication are not considered adverse events after treatment unless they reoccur after the subject has recovered from the pre-existing condition or they represent an exacerbation in intensity or frequency.

All reportable AEs will be assigned a relationship to the study drug by the principal investigator. A drug-related AE is an event with a plausible time relationship to drug intake that cannot be explained by the disease or other drugs.

Any AEs experienced by the subject, from the time of signing the Informed Consent Form through the completion of study participation, will be reported as described (see Section 11.3) and recorded on the CRF. If AEs are present when the patient completes study participation, the subject will be re-evaluated within two weeks of completion and the results of this re-evaluation will be recorded on the CRF. If AEs are not resolved, additional follow-up will be performed as appropriate. All reportable AEs must be reported to the RDCRN within **20 working days** of the notification of the event or of the site becoming aware of the event.

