12.2. Serious Adverse Events

A serious adverse event (SAE) is defined as any adverse event that results in any of the following outcomes:

- Death
- Life-threatening experience
- Required or prolonged inpatient hospitalization
- Persistent or significant disability/incapacity
- Congenital anomaly/birth defects

Life-threatening experience: Any adverse event that places the patient, in the view of the reporter, at immediate risk of death from the adverse event as it occurred, i.e., does not include an adverse event that had it occurred in a more severe form, might have caused death.

Persistent or significant disability/incapacity: The adverse event that resulted in a substantial disruption of a person's ability to conduct normal life functions.

Important medical events based upon appropriate medical judgment, that may jeopardize the patient or subject and may require medical or surgical intervention to prevent one of the outcomes listed above: Adverse events that may not result in death, be life-threatening, or require hospitalization may be considered a serious adverse event when, based upon appropriate medical judgment, they

may jeopardize the patient or subject and may require medical or surgical intervention to prevent one of the outcomes listed above.

The investigator will be asked to assess the severity of the adverse drug/biologic experience using the following categories: mild, moderate and severe. This assessment is subjective and the investigator should use medical judgment to compare the reported adverse event to similar type events observed in clinical practice. Below are listed guidelines for severity assessment:

- **Mild:** Symptom(s) barely noticeable to the subject/patient or does not make the subject/patient uncomfortable. The adverse event does not influence performance or functioning. Prescription drugs are not ordinarily needed for relief of symptom(s).
- **Moderate:** Symptom(s) of a sufficient severity to make the subject/patient uncomfortable. Performance of daily activities is influenced. Treatment of symptom(s) may be needed.
- **Severe:** Symptom(s) of a sufficient severity to cause the subject/patient severe discomfort. Severity may cause cessation of treatment with the study drug. Treatment for symptom(s) may be given.

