14.1. Subject withdrawal

A subject (or the legal guardian acting on behalf of the subject) is free to withdraw consent and discontinue participation in the study at any time, and without prejudice to further treatment, according to standard clinical practice. A subject who decides to discontinue participation in the study should be contacted to obtain information about the reason(s) for discontinuation and collection of any potential AEs.

All data acquired prior to termination for the reasons outlined below will be included in the primary analysis unless a participant withdraws consent. A subject's participation in the study may be discontinued at any time at the discretion of the investigator. The following may be justifiable reasons for the investigator to remove a subject from the study:

- The subject is uncooperative or non-compliant with the protocol.
- The subject develops an exclusion criterion or concurrent disease.
- The subject develops a condition or adverse event that, in the opinion of the investigator, contraindicates the continuation of treatment.
- The subject desires a surgical procedure or other alternative treatment for cognitive decline.

The reason for withdrawal should be clearly described. Withdrawn subjects may not re-enter the study. Follow-up procedures will be required if the subject discontinues as a result of an adverse event. Follow-up may include completing the study assessments scheduled at the final visit. Every effort will be made to conduct a final study visit with the participant, and participants will be followed clinically until, if applicable, all adverse events resolve.

If a subject or the subject's legal guardian, acting on behalf of the subject, discontinues participation in the study, or the subject is discontinued by the

investigator, the Patient Completion/Discontinuation Case Report Form (CRF) describing the reason for discontinuation must be completed. Any AEs experienced up to the point of discontinuation must be documented on the AE CRF. If AEs are present when the subject withdraws from the study, the subject will be re-evaluated within two weeks of withdrawal. If AEs are not resolved, additional follow-up will be performed, as appropriate.

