14.2. Termination of Subject Participation

The investigator may choose to terminate a subject's participation in the study at any time. Conditions that may warrant termination of study participation include, but are not limited to:

- The discovery of an unexpected, serious, or unacceptable risk to subjects enrolled in the study
- Insufficient adherence to protocol requirements.

Subjects who withdraw or are withdrawn from the study will not receive further evaluations unless warranted by an ongoing adverse event.

15. Risks to Subjects

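### When a pregnancy is found after an extension injection, withdrawal ends evaluations, and unless it is recorded as an adverse event only an attempted final visit could reveal its outcome

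*Combined protocol and SAP*

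**What the plan says.** **Pregnancy and withdrawal.** Section 6.1.1 excludes anyone "Pregnant or lactating, or considering pregnancy". Section 7.4 requires a urine test at baseline and at each visit, with the consequence that "Subjects testing positive will be withdrawn from the study".

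**After withdrawal.** Section 14.2 states: "Subjects who withdraw or are withdrawn from the study will not receive further evaluations unless warranted by an ongoing adverse event". Section 14.1 asks for every effort to hold a final visit. Its other provisions depend on an AE: "Follow-up procedures will be required if the subject discontinues as a result of an adverse event"; a re-evaluation within two weeks if AEs are present at withdrawal; and "participants will be followed clinically until, if applicable, all adverse events resolve". Among the reasons for removing a subject, 14.1 lists "The subject develops an exclusion criterion or concurrent disease", with a condition or AE that contraindicates treatment as a separate item.

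**What counts as an event.** Section 12.1 defines an AE as something a subject experiences during participation, and sets the recording window as "Any AEs experienced by the subject, from the time of signing the Informed Consent Form through the completion of study participation". Section 12.2 defines an SAE as an AE with one of several outcomes, including "Congenital anomaly/birth defects".

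**Reporting of the withdrawal.** Section 12.3 has subject terminations reported to the Principal Investigator within 24 hours. Section 14.1 requires a discontinuation form giving the reason. Section 9.3.2 summarises discontinuations by reason, and 12.6 gives the DSMB the number dropped with reasons.

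**Reproductive risk.** Section 15.5 says that this risk is unknown for Aldurazyme. Section 22 gives uncertainty about fetal harm as the reason for excluding pregnant women.

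**The concern.** Long-term safety is the first objective in Section 1. The protocol admits sexually active females of child-bearing potential who use two methods of birth control (6.2.1), doses every three months for five years, and names congenital anomaly as a serious outcome. Its withdrawal rule nevertheless stops evaluations when a pregnancy is detected, months before any anomaly at birth could be seen.

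A report could then show a withdrawal for pregnancy with no anomaly recorded, and a reader could not tell whether the outcome was normal or was never sought. What is at stake is complete reporting of one named type of serious event. No efficacy or safety estimate in Section 9 depends on it.

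**Working it through.** The plan gives no figure to reproduce. The check sets the provisions side by side for a subject who tests positive at a scheduled visit after Visit One.

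1. *Is she withdrawn?* Yes (7.4).
2. *Do evaluations continue?* Only if an AE is ongoing (14.2).
3. *Is pregnancy an AE?* The supplied text does not say so. It is an exclusion criterion (6.1.1), and 14.1 treats developing an exclusion criterion and developing an AE as different reasons for removal. The list of examples in 12.1 is open, so an investigator could record it as an AE.
4. *If it is recorded as an AE:* the 14.1 follow-up to resolution applies, and the gap does not arise.
5. *If it is not:* the required follow-up, the two-week re-evaluation and the follow-up to resolution are not triggered. The best-effort final visit remains, and it does not mention pregnancy outcome.
6. *Could another rule bring the outcome in?* Section 12.3 runs its 24-hour clock from the investigator's first knowledge of an SAE. Section 12.9 covers unanticipated problems affecting subjects or others, including some that are not AEs. Both act on what the investigator happens to learn, and neither tells anyone to ask.
7. *Would a late anomaly be a study SAE?* An SAE must first be an AE (12.2), and an AE belongs to the period of participation (12.1). A birth after withdrawal falls outside that period on a literal reading. The wording of 12.3 has no end date. The two are not reconciled.

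**How long the unmonitored interval could be.** The inputs are three-monthly visits (7.2) with a test at each (7.4). The assumptions, which are not in the documents, are a nine-month pregnancy carried to birth and 4.345 weeks per month.

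- Detected three months after conception: (9 − 3) × 4.345 = 26.1 weeks to birth.
- Detected at conception, a ceiling that cannot be reached because a urine test is not yet positive: 9 × 4.345 = 39.1 weeks.
- Interval between visits: 3 × 4.345 = 13.0 weeks.

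Injections are given at the same three-monthly visits. A pregnancy first found on schedule after Visit One would therefore have been conceived within about 13 weeks after an injection, or shortly before one if too early to test positive. In that second case the remaining time is slightly under 26 weeks.

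No probability of pregnancy is computed. The documents give neither a rate nor the number of subjects able to conceive, which could be zero.

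**The case against.** The strongest reply is that most of the machinery already exists. The investigator would hear of the termination within 24 hours, the form would carry the reason, the DSMB would see it, and the final tables would list it. This stands. A reader might infer that a pregnancy would go unreported, and the documents do not support that. Only active pursuit of the outcome is missing.

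A second reply is that an investigator may record the pregnancy as an AE, which brings in 14.1. This is correct, but it is discretion, and sites could differ.

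A third is that the provision may sit elsewhere. The consent pages, a part of Section 2 and parts of Section 15 were removed from the copy reviewed, and the Study Operations Manual and DSMB charter were not supplied. This stands as a limit: the point is that no such provision was found in the supplied text.

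A fourth is that one outcome would prove nothing. This is also true, partly because subjects may be receiving intravenous Aldurazyme as well (6.1.1), so an anomaly could not be attributed to the intrathecal route. The case for asking is complete reporting, not estimation of reproductive risk.

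**Conclusion.** The point holds in a narrow form. For a pregnancy found after an extension injection and not recorded as an AE, the stated rules end evaluations and, apart from an attempted final visit, direct nobody to learn the outcome. Whether an anomaly discovered after withdrawal would be a study SAE is unclear.

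The size is low. At most 6 subjects enrol, the number able to conceive is not given, and no planned estimate changes. The interval of roughly 26 to 39 weeks rests on the assumed gestation and on scheduled testing, and its upper end is only a bound.

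Two wider readings should be set aside. A positive baseline test is a different matter: that subject fails an inclusion criterion (6.2.1) before any extension dose, at least six months after completing MIRC-002 (Section 7). Nor is stopping injections on a positive test a fault. Given the stated uncertainty about fetal harm, it is sound.

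**What to change.** Keep withdrawal from dosing on a positive test. Add to 7.4, with a matching exception in 14.2, wording such as:

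> Any pregnancy detected after an extension injection will, with consent, be followed by telephone or records to its outcome; a congenital anomaly will be reported as an SAE even if identified after withdrawal.

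In the study report, state for each such pregnancy whether the outcome is known. No new rule for reporting the withdrawal itself is needed.

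The cost is this short addition to the protocol, a consent-form line if one is not already there, and one or two later contacts with a subject who has left the study. No visit or procedure is added. If the unavailable documents already contain the provision, a cross-reference in 7.4 and 14.2 is enough.
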